Appendix 11 Optical Coherence Tomography Angiography

SCOPE

Optical coherence tomography angiography (OCT-A) will be performed at the study sites with this capability by trained personnel who are certified by the central reading center. OCT-A imaging will be performed for each patient at the intervals specified in the protocol (see Appendix 1 and Appendix 2).

The OCT-A images of both eyes will be obtained at protocol-specified visits and will be forwarded to the central reading center.

EQUIPMENT

Equipment used during this study is described in the Central Reading Center Manual. The ability to transfer images to electronically exportable digital files is required (i.e., no printed OCT-A images will be sent to the central reading center).

PROCEDURES AND CERTIFICATION

The central reading center will provide the study manual and training materials. OCT-A operators, systems, and software will be certified prior to any evaluation of patients.

Appendix 12 Fluorescein Angiography

SCOPE

Fluorescein angiography (FA) will be performed at the study sites by trained personnel, when non-infectious intraocular inflammation is suspected and investigator considers it as an important part of the diagnostic work-up. Analysis (if applicable) will be performed by the central reading center.

EQUIPMENT AND DIGITAL IMAGING SYSTEMS

Digital angiograms must be used while conducting an angiographic evaluation for the study. Widefield FA or standard FA with peripheral sweeps is preferred, if available.

Film-based angiography is not acceptable.

PROCEDURES

Refer to the Central Reading Center Manual for details.

Appendix 13 Anterior Chamber Paracentesis and Aqueous Humor Sampling Procedures

An aqueous humor sample will be collected from the study eye after pretreatment intraocular pressure measurement, but prior to study drug administration, as indicated in Appendix 1 and Appendix 2. The anterior chamber paracentesis will be performed by a qualified physician by placing a drop of topical anesthetic on the cornea, passing a needle through the limbus into the anterior chamber, and removing approximately $100 \ \mu$ L of aqueous fluid and more volume, if possible without endangering patient safety at applicable patient visits. Samples will be collected with the kit provided by the central laboratory and shipped on dry ice to the central laboratory as soon as possible after the draw.

The following procedures will be used to minimize the risk of potential adverse events associated with aqueous humor sampling (e.g., endophthalmitis, corneal abscess, hyphema, cornea, lens, iris trauma).

Aseptic technique will be performed by clinic staff involved in the aqueous humor collection tray assembly, anesthetic preparation, and aqueous humor sample collection. In addition to the procedures outlined below, any additional safety measures in adherence to specific institutional policies associated with aqueous humor sample collection will be observed.

As per individual site investigator decision, patients may self-administer anti-microbial drops prior to and after aqueous humor sample collection.

Prepare a sterile field that includes the following supplies:

- 10% povidone iodine swabs
- Sterile surgical gloves
- 4×4 sterile pads
- 0.5% proparacaine hydrochloride
- 5% povidone iodine ophthalmic solution
- 1-cc syringe
- 27- or 30-gauge needle, 0.5 inches in length
- Sterile saline solution
- Per individual investigator discretion:
 - Sterile cotton-tipped applicators
 - Eyelid speculum
 - Sterile ophthalmic drape
 - Surgical face mask

FHTR2163—Genentech, Inc. 99/Protocol GR42558, Version 4

Appendix 13: Anterior Chamber Paracentesis and Aqueous Humor Sampling Procedures

Aqueous humor sampling should be performed using an aseptic procedure and sterile field as follows:

- Instill two drops of 0.5% proparacaine hydrochloride into the study eye
- Wait 90 seconds
- As per individual investigator discretion, instill two drops of anti-microbial drops
- Wait 5 minutes (only if anti-microbial drops are used)
- Instill two drops of 5% povidone iodine ophthalmic solution in the study eye
- Disinfect the peri-ocular skin and eyelid of the study eye

Scrub the eyelid, lashes, and peri-orbital skin with 10% povidone-iodine swabs, starting with the eyelid and lashes and continuing with the surrounding peri-ocular skin. Ensure that the eyelid margins and lashes are swabbed, and proceed in a systematic fashion from medial to temporal aspects.

- Instill two additional drops of 5% povidone iodine ophthalmic solution in the study eye
- After washing hands, put on sterile gloves
- Per investigator discretion, the investigator may place sterile ophthalmic drape to isolate the field and place the speculum underneath the eyelid of the study eye
- Collect the aqueous humor sample (approximately 100 μL) using the 27- or 30-gauge needle attached to the 1-cc syringe through a paracentesis inserted at the temporal paralimbal clear cornea on a horizontal angle in a plane above and parallel to the iris with the bevel of the needle facing away from the iris, paying strict attention to avoid contact with the patient's eyelashes, lens, or iris.

NOTE: The investigator and patient should refrain from talking, coughing, or sneezing during the aqueous sample collection. A surgical face mask may be worn per investigator discretion.

- Dispense collected aqueous humor into the appropriately labeled collection tube provided and store frozen until shipped as described in the laboratory manual
- As per individual site investigator decision, patients may self-administer anti-microbial drops prior to and after aqueous humor sample collection

Appendix 14 WHO Toxicity Grading Scale for Determining the Severity of Adverse Events

ITEM	Grade 1 Toxicity	Grade 2 Toxicity	Grade 3 Toxicity	Grade 4 Toxicity
HEMATOLOGY				
Hemoglobin	9.5–10.5 g/dL	8.0–9.4 g/dL	6.5–7.9 g/dL	<6.5 g/dL
Absolute Neutrophil Count	1000–1500/mm ³	750–999/mm ³	500–749/mm ³	< 500/mm ³
Platelets	75,000–99,000/mm ³	50,000–74,999/mm ³	20,000–49,000/mm ³	<20,000/mm ³
Prothrombin Time (PT)	1.01–1.25×ULN	1.26–1.5×ULN	1.51–3.0×ULN	> 3 × ULN
Activated Partial Thromboplastin (aPTT)	1.01–1.66×ULN	1.67–2.33×ULN	2.34–3×ULN	>3×ULN
Fibrinogen	0.75–0.99×LLN	0.50-0.74 imes LLN	0.25-0.49×LLN	<0.25×LLN
Fibrin Split Product	20–40 μg/mL	41–50 μg/mL	51–60 μg/mL	>60 µg/mL
Methemoglobin	5%–9.9%	10.0%-14.9%	15.0%–19.9%	>20%
LIVER ENZYMES				
AST (SGOT)	1.25–2.5×ULN	2.6–5×ULN	5.1–10×ULN	> 10 × ULN
ALT (SGPT)	1.25–2.5×ULN	2.6–5×ULN	5.1–10×ULN	> 10 × ULN
GGT	1.25–2.5×ULN	1.6–5×ULN	5.1–10×ULN	> 10 × ULN
Alkaline Phosphatase	1.25–2.5×ULN	1.6–5×ULN	5.1–10×ULN	> 10 × ULN
Amylase	1.1–1.5×ULN	1.6–2.0×ULN	2.1–5.0×ULN	>5.1×ULN
CHEMISTRIES				
Hyponatremia	130–135 mEq/L	123–129 mEq/L	116–122 mEq/L	<116 or mental status changes or seizures
Hypernatremia	146–150 mEq/L	151–157 mEq/L	158–165 mEq/L	> 165 mEq/L or mental status changes or seizures
Hypokalemia	3.0–3.4 mEq/L	2.5–2.9 mEq/L	2.0–2.4 mEq/L or intensive replacement Rx required or hospitalization required	<2.0 mEq/L or paresis or ileus or life-threatening arrhythmia
Hyperkalemia	5.6–6.0 mEq/L	6.1–6.5 mEq/L	6.6–7.0 mEq/L	> 7.0 mEq/L or life-threatening arrhythmia
Hypoglycemia	55–64 mg/dL	40–54 mg/dL	30–39 mg/dL	< 30 mg/dL or mental status changes or coma

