2.1 SAFETY OBJECTIVE (PRIMARY OBJECTIVE)

The safety objective for this study (primary objective) is to evaluate the long-term safety and tolerability of FHTR2163 on the basis of the following endpoints:

- Incidence and severity of ocular adverse events, with severity determined according to the scale in Section 5.3.3
- Incidence and severity of systemic (non-ocular) adverse events, with severity determined according to the WHO toxicity scale (or the alternative scale in Section 5.3.3, if appropriate)

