4.5.7 Laboratory, Biomarker, and Other Biological Samples

Fasting is not required prior to specimen collection. The specimens will be sent to a central laboratory. The central laboratory will either perform the analysis or send the samples to the Sponsor or a designee for analysis and/or storage.

Samples will be collected for the following analyses:

- Hematology: WBC count, RBC count, hemoglobin, hematocrit, platelet count, and differential count (neutrophils, eosinophils, basophils, monocytes, lymphocytes, and other cells)
- Chemistry panel (serum): sodium, potassium, glucose, BUN or urea, creatinine, total protein, albumin, total and direct bilirubin, ALP, ALT, and AST
- Coagulation: INR, aPTT, and PT
- Lipids: cholesterol, LDL cholesterol, HDL cholesterol, and triglycerides
- Pregnancy test

All women of childbearing potential will have a urine pregnancy test prior to each study drug injection. If a urine pregnancy test is positive, it must be confirmed by a serum pregnancy test.

- PK analysis (serum and aqueous humor)
- Immunogenicity analysis (serum)
- Exploratory biomarker research (plasma and aqueous humor)

Exploratory biomarker research may include, but will not be limited to, cleaved DKK3 and other biomarkers associated with HtrA1, GA, and/or AMD. Research may involve extraction of cell-free DNA.

For sampling procedures, storage conditions, and shipment instructions, see the laboratory manual.

Unless the patient gives specific consent for his or her leftover samples to be stored for optional exploratory research (see Section 4.5.8), biological samples will be destroyed no later than the time of completion of the final Clinical Study Report, with the following exceptions:

- Serum and aqueous humor samples collected for PK or immunogenicity analysis may be needed for additional immunogenicity characterization and for PK or immunogenicity assay development and validation; therefore, these samples will be destroyed no later than 5 years after the final Clinical Study Report has been completed.
- Blood and aqueous humor samples collected for biomarker research and biomarker assay development will be destroyed no later than 15 years after the final Clinical Study Report has been completed.

However, the storage period will be in accordance with the Institutional Review Board or Ethics Committee (IRB/EC)–approved Informed Consent Form and applicable laws (e.g., health authority requirements).

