Appendix 14: WHO Toxicity Grading Scale for Determining the Severity of Adverse Events

ITEM	Grade 1 Toxicity	Grade 2 Toxicity	Grade 3 Toxicity	Grade 4 Toxicity
CARDIAC DYSFUN	CTION (cont.)	·		
Hemorrhage, Blood Loss	Microscopic/occult	Mild, no transfusion	Gross blood loss, 1–2 units transfused	Massive blood loss, > 3 units transfused
RESPIRATORY				
Cough	Transient, no Rx	Treatment associated cough, local Rx	Uncontrolled	
Bronchospasm, Acute	Transient, no Rx <80%–70% FEV ₁ (or peak flow)	Requires Rx, normalizes with bronchodilator, FEV ₁ 50%–70% (or peak Flow)	No normalization with bronchodilator, FEV ₁ 25%–50% (or peak flow retractions)	Cyanosis: FEV ₁ <25% (or peak flow) or intubated
GASTROINTESTINA	AL.			
Stomatitis	Mild discomfort, no limits on activity	Some limits on eating/drinking	Eating/talking very limited	Requires IV fluids
Nausea	Mild discomfort, maintains reasonable intake	Moderate discomfort, intake decreased significantly, some activity limited	Severe discomfort, no significant intake, activities limited	Minimal fluid intake
Vomiting	Transient emesis	Occasional/moderate vomiting	Orthostatic hypotension or IV fluids required	Hypotensive shock or hospitalization required for IV fluid therapy
Constipation	Mild	Moderate	Severe	Distensions w/vomiting
Diarrhea	Transient, 3–4 loose stools/day	5–7 loose stools/day	Orthostatic hypotension or >7 loose stools/day or IV fluids required	Hypotensive shock or hospitalization for IV fluid therapy required
NEURO & NEUROM	USCULAR			
Neuro-cerebellar	Slight incoordination, dysdiadochokinesis	Intention tremor, dysmetria, slurred speech, nystagmus	Locomotor ataxia	Incapacitated
Mood	Mild anxiety or depression	Moderate anxiety or depression and therapy required	Severe anxiety or depression or mania, needs assistance	Acute psychosis, incapacitated, requires hospitalization
Neuro Control	Mild difficulty concentrating, no Rx, mild confusion/agitation, ADLs unaffected	Moderate confusion/agitation, some limitation of ADLs, minimal Rx	Severe confusion/agitation, needs assistance for ADLs, therapy required	Toxic psychosis, requires hospitalization

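### Appendix 14 places an alkaline phosphatase value of 1.6–2.5×ULN in both Grade 1 and Grade 2, and the protocol gives no rule for choosing between them

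*Combined protocol and SAP*

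**What the plan says.** Section 2.1 makes severity part of the primary endpoint: "Incidence and severity of systemic (non-ocular) adverse events, with severity determined according to the WHO toxicity scale", or the alternative scale of Section 5.3.3 where appropriate. Section 5.3.3 names Appendix 14 as the scale and keeps Table 2 for events that Appendix 14 does not list. Section 6.4 summarizes adverse events by toxicity grade, among other levels.

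Among the liver enzymes in Appendix 14, Grades 1 to 3 read:

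- "Alkaline Phosphatase 1.25–2.5×ULN 1.6–5×ULN 5.1–10×ULN"
- "GGT 1.25–2.5×ULN 1.6–5×ULN 5.1–10×ULN"
- "ALT (SGPT) 1.25–2.5×ULN 2.6–5×ULN 5.1–10×ULN" (the AST row has the same limits)

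Grade 4 is above 10×ULN in all four rows.

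The chemistry panel in Section 4.5.7 ends with "total and direct bilirubin, ALP, ALT, and AST"; GGT is not in it. For hemorrhage, Grade 3 is "Gross blood loss, 1–2 units transfused" and Grade 4 is "Massive blood loss, > 3 units transfused".

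**The concern.** A grading table should give each value exactly one grade. For ALP the Grade 2 range begins before the Grade 1 range ends, and ALP is a test this study collects. Under Section 5.3 the investigator assigns severity, and Section 4.1 expects about 360 patients at about 75 sites. Two sites could record the same ALP level as mild and as moderate, each following the protocol. Section 5.3.5.6 also asks for increases in grade to be recorded. A rise in ALP from 1.5 to 2.0×ULN during a persistent event may or may not count as an increase, depending on which range is read.

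**Working it through.** The plan states no figure to reproduce here, so the check compares the ranges directly. All limits come from Appendix 14, read as closed intervals, with > taken as strict.

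**1. ALP and GGT overlap.** Grade 1 is 1.25–2.5×ULN and Grade 2 is 1.6–5×ULN. The two share every value from 1.6 to 2.5×ULN, a width of 2.5 − 1.6 = 0.9×ULN. Grade 1 is 2.5 − 1.25 = 1.25×ULN wide, so the shared part is 0.9/1.25 = 72% of it. Grade 2 is 5 − 1.6 = 3.4×ULN wide, so the shared part is 0.9/3.4 = 26% of it. These are shares of interval width, not of patients or events.

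| Value (×ULN) | ALP, GGT | AST, ALT |
|---|---|---|
| 1.5 | Grade 1 | Grade 1 |
| 1.6 | Grades 1 and 2 | Grade 1 |
| 2.0 | Grades 1 and 2 | Grade 1 |
| 2.5 | Grades 1 and 2 | Grade 1 |
| 2.6 | Grade 2 | Grade 2 |

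**2. Other rows on the same basis.** Ten rows expressed as multiples of ULN were compared at the Grade 1/2 and Grade 2/3 boundaries: AST, ALT, GGT, ALP, amylase, bilirubin, BUN, creatinine, PT and aPTT. Only GGT and ALP overlap.

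**3. Which limit is inconsistent.** The appendix contains two clean patterns.

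| Rows | Grade 1 ends | Grade 2 starts |
|---|---|---|
| AST, ALT, BUN | 2.5 | 2.6 |
| Amylase, bilirubin, creatinine | 1.5 | 1.6 |
| ALP, GGT | 2.5 | 1.6 |

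ALP and GGT take the Grade 1 end from the first pattern and the Grade 2 start from the second. Moving the Grade 2 start to 2.6, or the Grade 1 end to 1.5, removes the overlap. The two corrections give opposite answers inside it: 2.0×ULN becomes Grade 1 under the first and Grade 2 under the second.

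**4. Whether another rule settles it.** Table 2 applies only to events absent from Appendix 14, and ALP and GGT are listed there. The alternative-scale clause in Section 2.1 leads back to that same restriction. No instruction to take the higher or lower grade was found.

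**5. Hemorrhage.** As extracted, 1 or 2 units give Grade 3, 3 units give no grade, and 4 or more give Grade 4.

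**The case against.** The strongest reply is that hardly any record will be affected, and most of that stands. GGT is not in the panel. The schedules in Appendices 1 and 2 draw chemistry only at Weeks 48, 96 and 144, at early termination, and at unscheduled visits if clinically indicated. Under Section 5.3.5.7 an abnormal value becomes an adverse event only if it meets a listed criterion. If it is a sign of a disease, only the diagnosis is recorded. That section's own example is raised ALP and bilirubin recorded as cholestasis, which Appendix 14 does not list, so Table 2 would grade it. Section 6.4 also summarizes laboratory evaluations, so the ALP level itself is not lost. The analyses are descriptive and rest on no formal sample size calculation. None of this gives a reported ALP event in the overlap a single grade.

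Three stronger readings are tempting, and the documents do not support them.

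- A reader might infer from AST and ALT that the Grade 2 limit is the error and should be 2.6. ALP and GGT do match AST, ALT and BUN in Grades 1, 3 and 4, which leans that way. The 1.5/1.6 pattern in three other rows leaves the alternative open, and the source scale is not available here.
- A reader might infer that the severity part of the primary endpoint is undefined. The contradiction is confined to one measured analyte over part of its range.
- A reader might treat the 3-unit transfusion gap as an established second defect. It rests on a single > sign read from a PDF. The extracted appendix shows no ≥ sign at all and has similar edge gaps: methemoglobin of exactly 20%, amylase between 5.0 and 5.1×ULN, and induration of exactly 10 cm. The adjectives gross and massive also give the investigator some guidance. It is a point to check in the source.

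**Conclusion.** The contradiction in the ALP row is real. A reported ALP event at 1.6–2.5×ULN has two permissible grades under the scale that defines systemic severity in the primary endpoint, and the protocol does not choose between them. The GGT row has the same fault but matters only if GGT is measured outside the protocol panel.

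The consequence is small. It is limited to Grade 1 versus Grade 2 for the few ALP values reported as adverse events in their own right, and incidence is unaffected. The documents give no expected frequency of such events, so no count can be stated.

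The conclusion assumes that the extracted limits match the source PDF. The same 1.6 appears in two adjacent rows, which makes a reading error unlikely. Which limit is inconsistent remains open. This is a minor correction to a reference table; no study calculation is in error.

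**What to change.** - Check the ALP and GGT rows against the source scale and correct whichever limit is inconsistent, so that the Grade 1 and Grade 2 ranges no longer overlap.
- Send sites a short note with the corrected rows.
- For ALP events already entered, query the investigator against the central laboratory value so that the corrected limit is applied consistently. Section 5.3 gives the severity assessment to the investigator, so a query is preferable to regrading by the sponsor.
- In the same check, confirm whether the Grade 4 hemorrhage entry should read ≥ 3 units rather than > 3 units.

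The cost is one table correction at the next amendment, one site communication and probably a handful of data queries. Visits, sampling and the analysis methods do not change.

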Appendix 14: WHO Toxicity Grading Scale for Determining the Severity of Adverse Events

ITEM	Grade 1 Toxicity	Grade 2 Toxicity	Grade 3 Toxicity	Grade 4 Toxicity
CHEMISTRIES (con	t.)			
Hyperglycemia (note if fasting)	116–160 mg/dL	161–250 mg/dL	251–500 mg/dL	> 500 mg/dL or ketoacidosis or seizures
Hypocalcemia (corrected for albumin)	8.4–7.8 mg/dL	7.7–7.0 mg/dL	6.9–6.1 mg/dL	< 6.1 mg/dL or life-threatening arrhythmia or tetany
Hypercalcemia (corrected for albumin)	10.6–11.5 mg/dL	11.6–12.5 mg/dL	12.6–13.5 mg/dL	> 13.5 mg/dL or life-threatening arrhythmia
Hypomagnesemia	1.4–1.2 mEq/L	1.1–0.9 mEq/L	0.8–0.6 mEq/L	<0.6 mEq/L or life-threatening arrhythmia
Hypophosphatemia	2.0–2.4 mg/dL	1.5–1.9 mg/dL or replacement Rx required	1.0–1.4 mg/dL intensive Rx or hospitalization required	< 1.0 mg/dL or life-threatening arrhythmia
Hyperbilirubinemia	1.1–1.5×ULN	1.6–2.5×ULN	2.6–5×ULN	> 5 × ULN
BUN	1.25–2.5×ULN	2.6–5×ULN	5.1–10×ULN	> 10 × ULN
Creatinine	1.1–1.5×ULN	1.6-3.0×ULN	3.1–6×ULN	>6×ULN or required dialysis
URINALYSIS				
Proteinuria	1+ or <0.3% or <3 g/L or 200 mg–1 g loss/day	2–3+ or 0.3%–1.0% or 3–10 g/L or 1–2 g loss/day	4+ or >1.0% or >10 g/L or 2–3.5 g loss/day	nephrotic syndrome or >3.5 g loss/day
Hematuria	Microscopic only	Gross, no clots	Gross+clots	Obstructive or required transfusion
CARDIAC DYSFUN	CTION			
Cardiac Rhythm		Asymptomatic, transient signs, no Rx required	Recurrent/persistent, no Rx required	Requires treatment
Hypertension	Transient increase, >20 mm, no Rx	Recurrent, chronic, >20 mm, Rx required	Requires acute Rx, no hospitalization	Requires hospitalization
Hypotension	Transient orthostatic hypotension, no Rx	Symptoms correctable with oral fluids, Rx	Requires IV fluids, no hospitalization required	Requires hospitalization
Pericarditis	Minimal effusion	Mild/moderate asymptomatic effusion, no Rx	Symptomatic effusion, pain, ECG changes	Tamponade, pericardiocentesis, or surgery required

Appendix 14: WHO Toxicity Grading Scale for Determining the Severity of Adverse Events

ITEM	Grade 1 Toxicity	Grade 2 Toxicity	Grade 3 Toxicity	Grade 4 Toxicity
CARDIAC DYSFUN	CTION (cont.)	·		
Hemorrhage, Blood Loss	Microscopic/occult	Mild, no transfusion	Gross blood loss, 1–2 units transfused	Massive blood loss, > 3 units transfused
RESPIRATORY				
Cough	Transient, no Rx	Treatment associated cough, local Rx	Uncontrolled	
Bronchospasm, Acute	Transient, no Rx <80%–70% FEV ₁ (or peak flow)	Requires Rx, normalizes with bronchodilator, FEV ₁ 50%–70% (or peak Flow)	No normalization with bronchodilator, FEV ₁ 25%–50% (or peak flow retractions)	Cyanosis: FEV ₁ <25% (or peak flow) or intubated
GASTROINTESTINA	AL.			
Stomatitis	Mild discomfort, no limits on activity	Some limits on eating/drinking	Eating/talking very limited	Requires IV fluids
Nausea	Mild discomfort, maintains reasonable intake	Moderate discomfort, intake decreased significantly, some activity limited	Severe discomfort, no significant intake, activities limited	Minimal fluid intake
Vomiting	Transient emesis	Occasional/moderate vomiting	Orthostatic hypotension or IV fluids required	Hypotensive shock or hospitalization required for IV fluid therapy
Constipation	Mild	Moderate	Severe	Distensions w/vomiting
Diarrhea	Transient, 3–4 loose stools/day	5–7 loose stools/day	Orthostatic hypotension or >7 loose stools/day or IV fluids required	Hypotensive shock or hospitalization for IV fluid therapy required
NEURO & NEUROM	USCULAR			
Neuro-cerebellar	Slight incoordination, dysdiadochokinesis	Intention tremor, dysmetria, slurred speech, nystagmus	Locomotor ataxia	Incapacitated
Mood	Mild anxiety or depression	Moderate anxiety or depression and therapy required	Severe anxiety or depression or mania, needs assistance	Acute psychosis, incapacitated, requires hospitalization
Neuro Control	Mild difficulty concentrating, no Rx, mild confusion/agitation, ADLs unaffected	Moderate confusion/agitation, some limitation of ADLs, minimal Rx	Severe confusion/agitation, needs assistance for ADLs, therapy required	Toxic psychosis, requires hospitalization

Appendix 14: WHO Toxicity Grading Scale for Determining the Severity of Adverse Events

ITEM	Grade 1 Toxicity	Grade 2 Toxicity	Grade 3 Toxicity	Grade 4 Toxicity
NEURO & NEUROMUSCULAR (cont.)				
Muscle Strength	Subjective weakness, no objective symptoms/signs	Mild objective signs/symptoms, no decrease in function	Objective weakness, function limited	Paralysis
OTHER PARAMETERS				
Fever: Oral, >12 hours	37.7°C–38.5°C or 100.0°F–101.5°F	38.6°C–39.5°C or 101.6°F–102.9°F	39.6°C–40.5°C or 103°F–105°F	>40.5°C or >105°F
Headache	Mild, no Rx therapy	Transient, moderate, Rx required	Severe, responds to initial narcotic therapy	Intractable, required repeated narcotic therapy
Fatigue	No decrease in ADLs	Normal activity decreased 25%–50%	Normal activity decreased > 50%, cannot work	Unable to care for self
Allergic Reaction	Pruritus without rash	Localized urticaria	Generalized urticaria, angioedema	Anaphylaxis
Local Reaction	Tenderness or erythema	Induration < 10 cm or phlebitis or inflammation	Induration > 10 cm or ulceration	Necrosis
Mucocutaneous	Erythema, pruritus	Diffuse, maculopapular rash, dry desquamation	Vesiculation, moist desquamation, or ulceration	Exfoliative dermatitis, mucous membrane involvement or erythema, multiforme or suspected Stevens-Johnson or necrosis requiring surgery

ADLs = activities of daily living; FEV₁=forced expiratory volume in 1 second; GGT=gamma-glutamyl transferase; LLN=lower limit of normal; Rx=prescription; ULN=upper limit of normal.
